In Specific Aim 1, we aim to demonstrate differences in propofol sensitivity across 2 patient cohorts based on the presence of absence of basal ganglia pathology (Parkinson disease [PD] and essential tremor, respectively). By characterizing and demonstrating differences in group level pharmacokinetic/pharmacodynamics of propofol (primary endpoints), we will provide evidence suggesting basal ganglia pathology is associated with differential response to propofol suggesting the basal ganglia are an important part of brain circuitry regulating consciousness. This aim will be completed entirely at UCLA.

In Specific Aim 2, we aim to characterize the temporal evolution of brain signals (recorded from the cortex and the basal ganglia) with propofol induced loss and recovery of consciousness to identify network level changes correlating with consciousness. All subjects will have PD and will be assigned to the same intervention of propofol administration and withdrawal, while we invasively record brain signals from key nodes in the hypothesized brain networks regulating consciousness. The primary endpoint/outcome will be neurophysiologic data.

In Specific Aim 3A, we aim to demonstrate the role of the basal ganglia in regulating consciousness by focally modulating the network with deep brain stimulation (DBS). Patient with PD and previously implanted DBS will be randomly assigned to undergo anesthetic induction either with or without DBS. Primary endpoint will be the characterization of the pharmacokinetics/pharmacodynamics with and without stimulation with PD. We expect to see shifts in the kinetics and dynamics associated with DBS, suggesting focal modulation of the circuit alters consciousness regulating circuitry of the brain.

In Specific Aim 3B, we will conduct a final clinical trial in which we will, as in Aim 3, record from the brain of patients undergoing DBS implantation, now with or without DBS on during both induction and emergence from propofol anesthesia. The primary outcome will be neurophysiological signals and observing perturbations of the evolution of the brain signals with vs without DBS.

2. Background.

- Describe past experimental and/or clinical findings leading to the formulation of your study.
- For research involving investigational drugs, describe the previously conducted animal and human studies.
- For research that involves FDA approved drugs or devices, describe the FDA approved uses of this drug/device in relation to your protocol.

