Specific Aim 1: The overall goal for this aim is to assess the population level pharmacokinetic-pharmacodynamic (PK-PD) model for propofol sedation in *PD patients (who have BG pathology) in contrast to a control group (essential tremor, ET, who do not have BG pathology)*. The PK-PD model will be used to predict the time course of plasma and effect site concentration of propofol and establish differential anesthetic sensitivity profiles. This assessment will be done during battery placement surgeries for individuals already implanted with DBS electrodes.

Specific Aim 2: These experiments will be performed during the initial DBS implantation surgery. The overall goal for this aim is to assess neural correlates, with specific attention to network parameters/states, during LOC/LOR and ROC/ROR using direct, high-resolution invasive recordings from the basal ganglia (GPi/GPe) and frontoparietal cortices in humans. *There is only one study group in this aim – PD patients (no stimulation of GPi/GPe).*

Specific Aim 3a: These experiments will be performed during the DBS generator exchange surgeries, as in Aim 1. All study participants will have PD in this set of experiments and results will be compared across *experimental cohorts (GPi vs GPe stim)* as well as to PD patients anesthetized with propofol off stimulation (from Aim 1). During data analysis, the rater will be blinded to stimulation assignment.

Specific Aim 3b: These experiments will be performed during the initial DBS implantation surgery. Recordings and behavioral assessments will be made during both induction and emergence of anesthesia with *either GPi or GPe stimulation*, comparing results with those acquired in Aim 2 (no stimulation). As in Aim 3a, the rater will be blinded to stimulation assignment.

4. Research Plan / Description of the Research Methods:

4.a. Provide a comprehensive narrative describing the research methods.

- 1) Provide the **order in which tests/procedures will be performed**,
- 2) Provide the **setting** for these events and a description of the **methods used to protect privacy** during the study.
- 3) Provide the **plan for data analysis** (include as applicable the **sample size calculation**)

Please respond to all components of this item, or clearly indicate which components are not applicable.

Some information in responses below is taken from grant protocol section 3 "Approach". See figures referenced and citations in grant protocol.

RESEARCH METHODS

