Target-Controlled Infusion (TCI) Anesthesia protocol. We will use a syringe pump controlled by STANPUMP implementing the Eleveld Pharmacokinetics-Pharmacodynamics (PK-PD) model for propofol as a TCI system to achieve plasma target propofol concentrations.⁵⁷ Two intravenous cannulae will be used in each patient, one for propofol infusion and one for blood draws. Supplemental oxygen will be delivered as needed by nasal canula. Propofol serum concentrations will be confirmed via blood sampling to confirm the TCI performance. Blood samples will be stored on ice until they can be centrifuged, and the plasma fraction isolated by centrifuge and stored at -20 deg C until analyzed. Propofol concentration will be determined by a high performance liquid chromatographic method (HPLC).⁵⁸ The attending anesthesiologist will be able to override the pump at any point should there be evidence of airway obstruction, hemodynamic compromise, or other clinical issue, though the long track record of safety of TCI systems outside of the United States suggests this should not be a major issue, and TCI models appear safe to use in PD patients.⁴⁷ Per prior published work⁴⁸, target effect-site concentration of propofol will be started at 1.4 µg/mL (below expected level required for LOC/LOR) and will be increased by 0.3 µg/mL with reassessment until endpoints are achieved. ROC/ROR will be assessed with gradual reduction in propofol dose as with assessment of relevant endpoints. Due to clinical and invasive neurophysiological requirements, in all cases, ROC/ROR will be evaluated after LOC/LOR.

Specific Aims 1 & 3a:

Data collection for these aims will occur during IPG placement / replacement surgery for individuals with DBS. Specific Aim 1 will occur solely at UCLA following these guidelines. Specific Aim 3a will be collected at both UCLA and UTSW following the same protocol.

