Surgeries are performed under monitored anesthesia care, using propofol anesthetic. Once patients are positioned, propofol is administered per a target-controlled infusion (TCI) anesthesia protocol detailed above. Participants will also complete the Behavioral Assessments outlined above. Assessment will be completed at the end of every propofol infusion (every 5 minutes). Blood draw will also occur at this time. If data is being collected for **Specific Aim 1**, no DBS stimulation will occur. If data is being collected for **Specific Aim 3a**, the patient will receive either GPi or GPe stimulation during study tasks. Once stable anesthesia is established, local anesthetic is infused and the generator is replaced, prior to closing the skin. Behavioral assessments will be made during induction and / or emergence.

Specific Aims 2 & 3b:

Data collection for these aims will occur during DBS implantation surgery. Data will be collected at UCLA and UTSW following the same protocol.

Surgical procedure Intraoperative Recordings (Specific Aim 2, 3). For DBS implantation for PD, the DBS lead is targeted to ventral posterolateral GPi using image-guided targeting (2-4 mm anterior, ¹⁹⁻²⁴ mm lateral, and 4-6 mm inferior to the mid-commissural point [MCP], Figure 4). All trajectories are confirmed with intraoperative microelectrode recordings, based on firing activity and kinesthetic tests⁵² in addition to intraoperative awake macrostimulation testing, clinically assessed by [name]. LFP will be recorded from deep brain targets from the DBS lead's four or eight contacts (dependent on clinical selection of DBS

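### Aim 3a's primary contrast is announced as randomized DBS versus no DBS, but the design and procedures give every Aim 3a patient stimulation and borrow the off group from single-site Aim 1

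*Combined protocol and SAP*

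**What the plan says.** **Section 1 (Purpose and objectives, Specific Aim 3A).** PD patients with implanted DBS "will be randomly assigned to undergo anesthetic induction either with or without DBS". The endpoint follows that contrast: "Primary endpoint will be the characterization of the pharmacokinetics/pharmacodynamics with and without stimulation with PD". A shift under stimulation is to be taken as evidence that focal modulation alters the circuitry regulating consciousness.

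**Section 3 (Study Design, Specific Aim 3a).** The groups are "experimental cohorts (GPi vs GPe stim" and the results are compared between these two cohorts "as well as to PD patients anesthetized with propofol off stimulation (from Aim 1". The rater is to be blinded to stimulation assignment during data analysis.

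**Section 4.a (Specific Aims 1 & 3a).** For Aim 1, "no DBS stimulation will occur". For Aim 3a, "the patient will receive either GPi or GPe stimulation during study tasks". On sites: "Specific Aim 1 will occur solely at UCLA following these guidelines", whereas "Specific Aim 3a will be collected at both UCLA and UTSW following the same protocol".

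**Section 4.a (Data Analysis and Sample Size).** Aim 3a repeats the Aim 1 pipeline: a sigmoid Emax fit, with Ce50 compared between groups through 95% confidence limits. No site term, stratification or UCLA-only comparison is given. Aim 3a is sized for two populations, which are not named, at about 24 per arm (48 evaluable, 58 recruited).

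**The concern.** Section 1 names an allocation that the design and procedures sections leave no room for. An Aim 3a patient who must receive GPi or GPe stimulation cannot be allocated to no stimulation. The affected contrast is the stated primary endpoint and carries the causal claim of the aim.

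Without random allocation, a difference in Ce50 between stimulated and unstimulated patients could reflect how patients entered Aim 1 rather than Aim 3a. The documents also show one concrete imbalance: UTSW supplies stimulated patients but no unstimulated ones. Any difference in Ce50 between sites would enter the stimulation effect, and recruiting more patients in the same pattern would not remove it.

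**Working it through.** **1. The passages side by side**

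| Item | Section 1 | Section 3 | Section 4.a |
|---|---|---|---|
| Aim 3a arms | DBS, no DBS | GPi, GPe | GPi or GPe for each patient |
| Off group | Within Aim 3A, by randomization | PD patients of Aim 1 | Aim 1 patients are unstimulated |
| Sites | Aim 1 entirely at UCLA | not stated | Aim 1 UCLA; Aim 3a UCLA and UTSW |
| Groups sized | not stated | not stated | Two, unnamed |

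Three ways of reconciling these were tried.

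- *Two randomized arms, on and off.* This fits Section 1 and the two-population sample size. It contradicts Section 3 and the procedures, and leaves no sized GPi-versus-GPe comparison.
- *Randomization across Aims 1 and 3a.* This is written nowhere. It sits badly with Section 1's description of four separate studies and with separate recruitment of 58 for each of the two aims. It could not cover UTSW patients, because Aim 1 does not run there.
- *Two stimulated arms plus borrowed controls.* This fits Section 3 and the procedures, but not the randomization in Section 1.

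No reading makes all the sections true.

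**2. The plan's own sample size**

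Inputs from Sample Size, Aim 3a: 20% difference in Ce50, 20% between-subject variability, 80% power. Two-sided 0.05 is assumed from the 95% limits.

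- n per arm = 2(1.960 + 0.842)² × (SD/difference)². With SD 0.20 this is 15.7, so 16.
- The plan adds a measurement error whose size it does not give. A total SD of 0.245 returns 24, which implies an error of √(0.245² − 0.20²) = 0.14, or about 14% of Ce50.
- Recruitment: 48 × 1.2 = 57.6, so 58.

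The 24 can be neither confirmed nor refuted, so both SDs are carried below.

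**3. Illustration of the site imbalance (inputs assumed)**

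Bias = UTSW share of stimulated patients × site shift in Ce50. Standard error for 24 versus 24 = SD × √(1/24 + 1/24). Two-sided type I error = Φ(−1.96 + bias/SE) + Φ(−1.96 − bias/SE). The UTSW share is set at 50%, with no true DBS effect and no site adjustment.

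| Assumed site shift | Bias | Type I error, SD 0.20 | Type I error, SD 0.245 |
|---|---|---|---|
| 5% | 0.5 × 5% = 2.5% | 7% | 6% |
| 10% | 0.5 × 10% = 5% | 14% | 11% |
| 20% | 0.5 × 20% = 10% | 41% | 29% |

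With UTSW shares from 25% to 75% and the same shifts, type I error runs from 5% to 74% over both SDs.

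**4. Precision if the contrast is confined to UCLA**

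With 24 off and, at an assumed 50% share, 12 stimulated at UCLA:

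- SE ratio to 24 versus 24 = √[(1/24 + 1/12)/(1/24 + 1/24)] = √1.5 = 1.22.
- Power at SD 0.20 = Φ(0.20/(0.20 × √0.125) − 1.96) = Φ(0.87) = 81%.
- Power at SD 0.245 = Φ(0.20/(0.245 × √0.125) − 1.96) = Φ(0.35) = 64%.

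If all 48 evaluable Aim 3a patients are stimulated, 24 per target, then 24 versus 12 is the comparison of one target with off. Both targets pooled against off would keep about 24 versus 24.

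**The case against.** The best reply is that this is a conflict of wording. Section 3 openly states the use of Aim 1 controls. Both sites follow one protocol, with one infusion model and one assay method, so a large site difference is not to be expected. Some of the methods text is taken from a grant application that is not included here and may describe the allocation. UCLA can supply both stimulated and unstimulated patients, so a within-site comparison is available.

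Much of this stands, and it limits what can be said.

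- A reader might infer that unstimulated patients are in fact never randomized. The documents do not show what was done. They show that the sections disagree, and what follows if Sections 3 and 4.a govern.
- A reader might infer that stimulation and site are fully confounded. They are not: the confounding is partial, and the GPi-versus-GPe comparison does not use the Aim 1 controls, although its allocation method is not described either.
- A reader might add differences in assay, rater or calendar time. No passage says that assays or raters differ between the aims, or that Aim 1 enrols first. These are possibilities only.
- A reader might conclude that the rater will recognise Aim 1 recordings as unstimulated. Section 4.a says that data are de-identified at once, and nothing says that raters see the aim. The fair point is that the blinding procedure is not described.

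The reply does not restore the randomization. Blinded rating does not create random allocation, and a common protocol does not supply unstimulated patients at UTSW. A site-adjusted or UCLA-only contrast is possible, but the plan does not specify one.

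**Conclusion.** The concern holds in a conditional form. Section 1 states a randomized on-versus-off comparison for the primary endpoint of Aim 3a, and Sections 3 and 4.a describe a design that cannot deliver it. If those later sections govern, stimulation versus off is non-randomized and partly confounded with site, with no site term in the analysis. This conclusion rests on the text alone and would stand even if the two sites had identical Ce50.

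The size of the site bias is not known. The range of 2.5-10% of Ce50 is an illustration from an assumed UTSW share of 50% and assumed site shifts of 5-20%. Neither input is in the documents, and the top of the range supposes a site difference as large as the whole planned effect. At the mild end, type I error barely moves (6-7%). The contradiction must be fixed before the contrast is reported as randomized. The particular redesign is a matter of choice.

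**What to change.** 1. Reconcile Section 1, Section 3, the Aims 1 & 3a procedures and the Aim 3a sample size on the arms, how patients are allocated to each, and which two populations were sized.
2. Either randomize off-stimulation in fact, or delete the claim. One way to randomize is a single concurrent allocation list at UCLA covering the Aim 1 PD and Aim 3a patients who are eligible for all arms. Common eligibility needs stating, because Section 3 requires only implanted DBS electrodes for Aim 1. Otherwise, label stimulation versus off as non-randomized.
3. In either case, estimate stimulation versus off within UCLA or with site as a stratum, so that UTSW informs only GPi versus GPe. State how GPi or GPe is assigned.
4. Code Aim 1 PD and Aim 3a recordings together before blinded rating, and say so.
5. Restate the power for stimulation versus off on the patients who inform it.

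**Cost.** A protocol amendment and, if randomizing across the aims, an allocation list with concurrent enrolment at UCLA. No extra patients are strictly required, but precision falls: 24 off versus 12 stimulated gives power of about 81% at SD 0.20 or 64% at SD 0.245.

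Placing a separate randomized off arm inside Aim 3a at 24 per arm would instead need 3 × 24 = 72 evaluable patients. That is 72/0.8 = 90 recruited (87 by the plan's 1.2 multiplier), against the planned 58.

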For all specific aims:

Prior to conducting any research related tests / procedures, the patient will be consented. The consent process will be facilitated by the IRB approved research coordinator and will occur in a private room in the pre-operative area prior to surgery. Once in the operating suite, the patient will be put under anesthesia for clinical purposes for surgery. Privacy will be maintained by limiting the individuals in the operating room to only necessary IRB approved research personnel. In addition, all data collected during the study will be immediately de-identified and stored on an encrypted, password protected server.

Behavioral Assessments. For each experiment, three behavioral responses will be evaluated: (1) loss/recovery of spontaneous movement (i.e., loss and recovery of responsiveness (LOR/ROR)) (2) loss/recovery of movement in response to stimuli (separately to clicks [non-salient] and verbal stimuli [salient], as per prior work by Purdon and colleagues⁴), and (3) loss/recovery of movement to command (verbal command with patient name with instruction to show different numbers of fingers, as proxy of loss/recovery of consciousness (LOC/ROC)). Stimuli will be presented in an interleaved fashion every 4 seconds binaurally via headphones (15 presentations of each stimuli at each dose, total 5 min per dose, or until failure to respond 3 times in a row to a certain stimulus). We use these separate measures because of the literature and our hypothesis that circuits mediating responsiveness and consciousness are separable. Namely, numerous studies highlight that consciousness (defined as ability to interact with the environment, most often measured by the isolated forearm test) can be maintained even with loss of responsiveness.^{39, 56}

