Behavioral data analysis and constructing propofol dose response curve. Behavioral data will be collected from both PD and ET patients undergoing generator replacement surgery. Propofol will be administered using a recently published, unified PK-PD for propofol developed to predict the BIS (bispectral index) response to propofol for a broad, diverse population by Eleveld and colleagues, which includes age adjustment, allometric scaling, and parameters for arterial and venous sampling.⁵⁷ (Although not a focus of our work and its value questionable given our underlying hypothesis of altered mesocircuit function in PD, we will record BIS in all patients as an additional data point.) From a range of studies, we expect that in a healthy population loss of responsiveness in 50% of healthy patients will occur with an age-adjusted effect site concentration (Ce₅₀) between 2.71–3.44 µg/ml.⁷⁴ The only published pharmacodynamic studies in PD patients reported a Ce₅₀ of 2.05 and 2.28 µg/ml.^{47, 48} We therefore expect that the dose-response curve for PD patients will be shifted to the left compared to ET patients, who lack basal ganglia pathology. To test this hypothesis, propofol infusion will be initiated with an effect-site concentration (Ce) target of 1.4 µg/ml for 5 min, incremented by 0.3 µg/ml steps every 5 min until loss of behavioral responses (as defined in 3.1.4). One additional incremental step will be performed after loss of responses. Venous serum samples will be drawn at the end of each 5 min step before the next increment. After conclusion of the procedure, target Ce would decrement by 0.3 µg/ml every 5 min until recovery of behavioral responses. Serum sampling will be used to confirm that the Eleveld unified TCI model is functioning as predicted.

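### The three-miss stop on stimulus testing is not limited to induction; on descending steps it can end command testing early, so that recovery of consciousness is recorded late

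*Combined protocol and SAP*

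**What the plan says.** Section 4.a, Behavioral Assessments, describes a single procedure for loss and recovery alike. Three kinds of stimulus can be identified: clicks, verbal stimuli, and a spoken command whose endpoint, "loss/recovery of movement to command", is the proxy for loss and recovery of consciousness (LOC/ROC). Spontaneous movement is listed separately as the marker of responsiveness (LOR/ROR) and needs no stimulus.

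On timing: "Stimuli will be presented in an interleaved fashion every 4 seconds binaurally via headphones". The planned amount is "15 presentations of each stimuli at each dose, total 5 min per dose". An early stop is attached to this, under which testing runs for that long "or until failure to respond 3 times in a row to a certain stimulus". The text does not say whether three misses end that stimulus or the whole block, whether testing restarts within the step, or whether the stop is meant for induction only.

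Other places bear on the descending limb:

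- The Target-Controlled Infusion paragraph places recovery after loss in all cases and gives no separate stimulus rule for it.
- Data Analysis, Specific Aim 1, adds one further step after responses are lost, then lowers the target by 0.3 µg/ml "every 5 min until recovery of behavioral responses".
- The surgical timeline for Aims 2 and 3b uses the same task during induction and emergence.
- The Aims 1 and 3a text places assessment at the end of each 5-minute infusion and makes emergence testing optional.

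**The concern.** A stop after three misses suits the ascending limb, where the aim is to find when responses disappear. On the descending limb the patient has already lost responses, so until recovery each step opens with misses. Followed literally, the rule ends stimulus and command testing near the start of the block. A patient who could obey the command later in that step is not tested until the next, lower one.

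Three things are at stake:

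- **ROC timing in Aims 2 and 3b.** Section 1 says Aim 2 follows "propofol induced loss and recovery of consciousness to identify network level changes correlating with consciousness". If ROC is marked late, some ECoG/LFP data treated as unconscious come from minutes in which the patient would have responded.
- **Absolute recovery concentration**, which is recorded too low.
- **The gap between ROC and ROR.** The protocol measures them separately because it expects their circuits to be separable. Spontaneous movement can be seen throughout, while the command is tested only briefly. The rule can therefore make ROC look later relative to ROR for procedural reasons.

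**Working it through.** **1. The plan's block length.** Inputs from Behavioral Assessments: one stimulus every 4 s, 15 of each, 5 min per dose.

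- Block length = types × 15 × 4 s. Three types: 3 × 15 × 4 = 180 s. The stated 5 min is not reproduced.
- Five minutes would need 300 / 4 / 15 = 5 types, but only three are named. Both are carried below.

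**2. Time to the stop, for a patient who misses everything (strict rotation).**

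- First type to fail: third miss begins at 2 × types × 4 s = 24 s (three types) or 40 s (five). Adding its 4-s slot gives 28 s or 44 s.
- All types failed: 3 × types × 4 s = 36 s (three) or 60 s (five).
- If a stop ends only the failed stimulus, the command still meets its own third miss by 36 s or 60 s.

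**3. Mean recording delay.** Assume a 300-s step, testing from its start until time t, and recovery uniform within the step. Recovery after t is picked up when the next step begins, so mean delay = (300 − t)² / 600.

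| Types | Testing ends at t | Mean delay |
|---|---|---|
| Three, first type fails | 28 s | 272²/600 = 123 s |
| Three, all fail | 36 s | 264²/600 = 116 s |
| Three, all 15 presented | 180 s | 120²/600 = 24 s |
| Five, first type fails | 44 s | 256²/600 = 109 s |
| Five, all fail | 60 s | 240²/600 = 96 s |
| Five, all 15 presented | 300 s | 0 s |

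The stop adds 116 − 24 = 92 s to 123 − 24 = 99 s with three types, and 96 to 109 s with five.

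**4. Recorded target.** If Ce falls linearly over the full 5 min and recovery is assigned to the step target (both assumptions), missing a step costs 0.3 µg/ml.

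- Three types: 0.3 × 264/300 = 0.264 with the stop and 0.3 × 120/300 = 0.12 without, so the stop adds about 0.14 µg/ml.
- Five types: 0.3 × 240/300 = 0.24 with the stop and 0 without.

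**5. Simulation of the descending staircase.** Assumptions outside the documents: exponential approach to each target with half-time 60 or 150 s, recovery thresholds uniform over 1.8–2.6 µg/ml, response probability 0.7 or 1.0 below threshold, and a stop once all types have three misses. Recovery is the first response to the command. Each cell gives values without the stop, then with it; the concentration columns show how far the recorded value falls too low.

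| Block | Mean delay, s | Step target, µg/ml | Ce at detection, µg/ml |
|---|---|---|---|
| Three types, start of step | 12–34; 141–152 | 0.02–0.09; 0.20–0.26 | 0.01–0.03; 0.10–0.13 |
| Three types, end of step | 37–75; 91–117 | 0.00–0.01; 0.03–0.11 | 0.05–0.11; 0.12–0.14 |
| Five types, fills the step | 9–18; 92–134 | 0.00–0.01; 0.13–0.23 | 0.01–0.03; 0.07–0.12 |

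With half-time 0 (Ce at target at once) the stop adds no delay and no bias in any arrangement.

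**The case against.** The best defence is that three misses in a row reads naturally as a criterion for loss, that the descent is said to continue until responses recover, and that the staff may never intend the stop to operate there. That may be so, but the sentence applies at each dose, the paragraph covers recovery, and no passage exempts the descent.

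Several limits on the point do stand:

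- The Aims 1 and 3a text can be read as end-of-step testing. With a three-type block the effect is then smaller. No such sentence appears for Aims 2 and 3b.
- The Aim 2 analysis paragraph names LOC/LOR only, so no ROC-aligned analysis is spelled out. Recovery is nevertheless in that aim's stated purpose, and emergence is recorded.
- The 5-min descending step is given under Aim 1. Applying it to Aims 2 and 3b rests on the general 5 min per dose.
- The documents do not say that recovery is assigned to the step target. The model is written in terms of Ce, and on that scale the simulated error from start-of-step testing is about half as large.

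A reader might infer that testing always stops 36 s into a step and that the rule alone leaves 264/300 = 88% of it untested. The documents do not support this: 36 s needs three rotating types that must all fail, and on that basis 120/300 = 40% of the step is untested even without the stop.

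**Conclusion.** The point holds as a flaw in a stated rule: followed as written on the descending limb, it cuts short the testing of recovery to stimuli and to command. Expected delay is about 96–123 s, against 0–24 s with full presentation. This assumes that testing starts with a 5-min step, Ce is still falling, and recovery is uniform within the step. The delay is smaller for a 180-s block at the end of the step, and the stop adds nothing if Ce reaches target at once.

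A reader might go further and conclude that all recovery endpoints are biased, or that the planned 20% Ce50 difference is threatened. Neither follows. ROR by spontaneous movement is untouched. All groups share the rule, so a common shift largely cancels in the PD–ET and stimulation comparisons. The harm lies mainly in ROC timing against ECoG/LFP in Aims 2 and 3b, in the absolute recovery concentration, and in the apparent separation of ROC from ROR. The change should be made because responses in untested minutes cannot be reconstructed afterwards.

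**What to change.** In Behavioral Assessments:

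- State that the three-miss stop does not apply on descending steps, present all 15 of each stimulus there, and score recovery separately for each stimulus.
- On ascending steps, state that three misses end only that stimulus, so that missed clicks cannot end testing of the command.
- Reconcile 3 × 15 × 4 s = 180 s with the stated 5 min: name any further stimulus types, or correct the count, interval or duration.
- Reconcile this paragraph with the end-of-step timing in the Aims 1 and 3a text, and say where in the step the block sits for each aim.

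A mirrored criterion of three consecutive responses for recovery would be a reasonable preference but is not needed to cure the problem.

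The cost is protocol wording and a change to the BCI2000 presentation script. Unresponsive patients receive more presentations. Steps are already stated as 5 min, so no step time is added and no dosing changes.
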